## 7.2 Study Periods

### 7.2.1 Screening Period

Assessing patient's suitability for enrollment based upon defined inclusion and exclusion criteria. The informed consent process and enrollment will occur during this period after which preoperative demographics and study defined covariates will be recorded.

### 7.2.2 Baseline Acquisition Period

Following randomization using an envelope randomization technique to either the control or intervention cohort enrolled subjects will undergo baseline testing with the MMSE and CAM assessment tools. Subsequently all subjects will have acquisition of bifrontal NIRS cerebral oximetric readings on both room air and with 100% oxygen supplementation. The control group and the intervention group will have open NIRS baseline data collection. This will allow all enrolled subjects to demonstrate that a set of baseline rSO2 values can be obtained and thus reduce the probability of unreadable outliers (i.e. subjects with anomalously located frontal sinuses) being studied in the control group. The baseline acquisition will occur in the operating room just prior to anesthesia induction.

[figure not shown]
### 7.2.3 Intraoperative and Immediate Postoperative Period

The intraoperative period will occur immediately following completion of the Baseline Acquisition Period. Subjects randomized to the control group will be induced into general anesthesia with electronically blinded rSO2 monitoring while those randomized to the intervention cohort will undergo open rSO2 monitoring with the application of a standardized interventional protocol (Appendix D) for any observed significant cerebral desaturations. Significant cerebral desaturations are defined as any desaturation  $\geq 10\%$  of established room air baseline values for each individual subject. This period will continue through the end of the surgical procedure to PACU discharge or if the subject goes to the ICU through the first 12 hours of ICU admission.

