### **6.3 Secondary Objectives**

Secondary objectives of this pilot study include the following:

- 1) Assess the frequency of cerebral desaturations in both the intervention and control cohorts by examining both the total number of patients experiencing any cerebral desaturation as well as the total number of events among patients experiencing any cerebral desaturation (of at least 5% below baseline and progressively larger desaturations). These analyses will be conducted on the entire study population as well as upon each cohort. The Area Under the Curve (AUC) analysis

technique [incremental desaturation categories will be assessed based upon 5 to 50% decreases, measured in 5% increments, from established room air baseline as well as oxygen supplemented pre-incision baselines as well as desaturations below absolute measured rSO2 values] will be employed to conduct these analyses.

- 2) Assess the frequency of adverse clinical events and serious adverse events overall and in each cohort.
- 3) Perform a comprehensive assessment of the frequency and efficacy of predefined rSO2 desaturation mitigation interventions and their collective ability to affect the observed cerebral oximetry values.
- 4) Assess the interventional cohort's preoperative demographics and collected covariates for association with the ease or difficulty of mitigating observed cerebral desaturation events.

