### **7 STUDY DESIGN**

#### **7.1 Study Design**

This study is a single center (University Hospitals Case Medical Center), prospective, randomized, controlled pilot study of elderly thoracic surgical patients undergoing procedures involving the use of SLV. A total of 100 eligible subjects will be randomized in a balanced fashion (1:1) to either the control cohort that will have electronically blinded bi-frontal cerebral oximetry monitoring or the intervention cohort that will have open bi-frontal cerebral oximetry monitoring with a predefined intervention protocol for observed desaturations of greater than 20% of established oxygen supplemented baseline values (see Appendix C). Both the control and intervention groups will have baseline NIRS data obtained in an unblinded fashion. The study will be divided into four separate periods that include screening, baseline acquisition, intraoperative and immediate postoperative and the postoperative follow up period.

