## **10 TREATMENT OF SUBJECTS**

### **10.1 Study Device**

The study device, INVOS® 5100C, is described in Section 8. Enrolled subjects will be randomized in a balanced fashion (1:1) to either the control group (blinded cerebral oximetry monitoring intraoperatively and in the immediate postoperative period) or to the intervention group (open cerebral oximetry monitoring with the use of a standardized intervention protocol for observed desaturations greater than 20%).

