### **10.3 Intervention Group**

The intervention group will have baseline NIRS values obtained in a manner analogous to the control group. Following recording of the baseline values the subjects will be induced into general anesthesia and the clinicians as well as an IRB registered research assistant will be able to openly monitor the NIRS data. Upon observed cerebral desaturations greater than 20% of the oxygen supplemented baseline on either frontal hemisphere the research assistant will inform the anesthesia clinician that a significant cerebral desaturation is occurring and requires treatment. At this point a standardized interventional protocol will be followed that is detailed in Appendix C. The clinicians caring for the subject will have the ability to override the study intervention algorithm based upon the patient's physical condition at the time.

The intervention protocol for observed desaturations >20% will involve insuring that the subject's head vessels are not kinked or obstructed, increasing the mean arterial pressure via an intravenous fluid bolus or administration of a vasoconstrictor (i.e. phenylephrine or ephedrine) as deemed appropriate by the anesthesia clinician caring for the subject, normalizing PaCO2 to a value between 40 to 50 mmHg, or alternatively normalizing end tidal CO2 to a value of 35 to 45 mmHg. Subsequent interventions may include increasing the FiO2, especially if the SpO2 is below 98% or administering an intravenous inotropic agent if a low flow state is suspected. Administration of an inotrope will occur as judged by the clinician caring for the subject. Finally, in cases where the subject's hematocrit is known or suspected to critically low transfusion of allogeneic blood will be considered. The decision to transfuse allogeneic blood will be made by the anesthesia and surgery clinicians caring for the subject.

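### Section 7.2.3 starts the intervention protocol at a 10% fall from the room-air baseline, while sections 7.1 and 10.3 start it at a fall of more than 20% from the oxygen-supplemented baseline.

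*Combined protocol and SAP*

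**What the plan says.** Four sections of the combined protocol and SAP describe when the intervention protocol applies.

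- **Section 7.2.3** (study periods) gives the intervention cohort open monitoring with a "standardized interventional protocol (Appendix D) for any observed significant cerebral desaturations. Significant cerebral desaturations are defined as any desaturation" of at least 10% "of established room air baseline values for each individual subject".
- **Section 7.1** (study design) ties the intervention protocol to "desaturations of greater than 20% of established oxygen supplemented baseline values (see Appendix C", closing the parenthesis there.
- **Section 10.3** (intervention group) is the operational text: "Upon observed cerebral desaturations greater than 20% of the oxygen supplemented baseline on either frontal hemisphere the research assistant will inform the anesthesia clinician". The message passed on in that call is "that a significant cerebral desaturation is occurring and requires treatment". The section then lists the treatment steps for falls of more than 20% and points to Appendix C.
- **Section 10.1** (study device) refers to a "standardized intervention protocol for observed desaturations greater than 20" per cent and does not name a baseline.

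Both baselines are recorded for every subject, first on room air and then on 100% oxygen (sections 7.2.2 and 11.2.4). Secondary objective 3 in section 6.3 begins "Perform a comprehensive assessment of the frequency and efficacy of predefined" mitigation interventions. Objective 4 looks for covariates associated with the "ease or difficulty of mitigating observed cerebral desaturation events".

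**The concern.** The trigger is the working part of the experimental arm. It tells the research assistant when to call and the anesthesia clinician when to begin an algorithm that can lead to fluids or a vasoconstrictor and, under further conditions, to an inotrope or transfusion. With two triggers in force, the same action on the same reading can comply with one section and breach another. Section 14 requires the trial to be conducted as the protocol describes, and here there are two descriptions.

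Three things are at stake:

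- **Adherence** cannot be judged without knowing which events called for treatment.
- **Objectives 3 and 4** ask how often the interventions were used, how well they worked and how hard desaturations were to reverse. If efficacy or difficulty is expressed per event that should have been treated, the denominator depends on the rule.
- **The larger trial** needs one defined trigger to carry forward, and supplying its design is this pilot's stated purpose.

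Vasopressor and inotrope time and dose, and red-cell units, also appear among the primary endpoint variables in section 7.4.1. The trigger can therefore act directly on some endpoint values, and only in the intervention arm.

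**Working it through.** **Step 1: compare the rules.**

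| Section | Size of fall | Reference baseline | Hemisphere | Appendix cited |
|---|---|---|---|---|
| 7.2.3 | at least 10% | room air | not stated | D |
| 7.1 | more than 20% | oxygen-supplemented | not stated | C |
| 10.1 | more than 20% | not stated | not stated | none |
| 10.3 | more than 20% | oxygen-supplemented | either | C |

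Section 7.2.3 conflicts with 7.1 and 10.3 on both the percentage and the baseline. Section 10.1 is silent on the baseline, which is a gap and not a further conflict. The appendix letters differ. That may be a lettering slip, and the appendices are not in the available text, so nothing is inferred from it.

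**Step 2: can the 10% rule be an analysis category only?** No. Section 7.2.3 attaches its definition directly to applying the protocol, and 10.3 uses the same term, significant, for its own call to treat. The analysis categories are listed separately in sections 6.3 and 7.4.1. No available section presents the two rules as an alert level and a treatment level, or as intraoperative and postoperative versions.

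**Step 3: how far apart are they?** The plan gives no rSO2 values and no figure to reproduce, so this is an illustration. Let b be the room-air baseline and r the proportional rise on oxygen, both assumed, and read both percentages as relative falls.

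- 7.2.3 cut-off: 0.9 × b
- 7.1/10.3 cut-off: 0.8 × b × (1 + r)
- Equal when 0.9 = 0.8 × (1 + r), so r = 0.9/0.8 − 1 = 0.125, whatever b is
- 7.1/10.3 cut-off as a fall from room air: 1 − 0.8 × (1 + r)

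The 7.2.3 cut-offs are 54.0, 58.5 and 63.0 for b = 60, 65 and 70. The last three columns give the 7.1/10.3 cut-off and, in brackets, the 7.2.3 cut-off minus it.

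| r | 10.3 trigger as fall from room air | b = 60 | b = 65 | b = 70 |
|---|---|---|---|---|
| 0% | 20% | 48.0 (+6.0) | 52.0 (+6.5) | 56.0 (+7.0) |
| 5% | 16% | 50.4 (+3.6) | 54.6 (+3.9) | 58.8 (+4.2) |
| 10% | 12% | 52.8 (+1.2) | 57.2 (+1.3) | 61.6 (+1.4) |
| 12.5% | 10% | 54.0 (0.0) | 58.5 (0.0) | 63.0 (0.0) |
| 15% | 8% | 55.2 (−1.2) | 59.8 (−1.3) | 64.4 (−1.4) |
| 20% | 4% | 57.6 (−3.6) | 62.4 (−3.9) | 67.2 (−4.2) |

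A positive gap means 7.2.3 would treat earlier, and a negative gap means 10.3 would. Despite its smaller percentage, 7.2.3 is the more sensitive rule only when oxygen raises the baseline by less than 12.5%.

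**The case against.** The strongest reply is that the working rule is clear in practice. Section 10.3 is the only text that says who acts, on what signal and on which hemisphere. Sections 7.1 and 10.1 agree with it on 20%, and 7.2.3 is an overview and the lone outlier. One designated assistant issues the alert, so haphazard use of two rules is possible but not shown to be likely. The unseen appendix may already state the right trigger.

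Crossing the threshold also does not by itself deliver drugs or blood. The first step listed is a check of the head vessels. Fluids and vasoconstrictors are at the clinician's discretion, inotropes and transfusion need further indications, and the clinician may override the algorithm.

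On the analysis side, open versus blinded monitoring remains a valid randomized comparison, and the group comparisons in section 15 do not use the trigger as a variable. Stored rSO2 and both baselines allow events to be recounted under either rule. Section 6.3 does not itself specify a per-qualifying-event denominator for objectives 3 and 4. Every rSO2 value in the illustration is assumed, and at a 10% oxygen rise the gap is only 1.2 to 1.4 points.

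All of this limits the damage, and most of it stands. It does not remove the contradiction. No available sentence gives 10.3 precedence. Clinician override does not tell the assistant when to call. A correct appendix would still leave 7.2.3 wrong. Recounting events afterwards cannot show which rule staff were following, or supply treatment that was not given.

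**Conclusion.** The concern holds. Section 7.2.3 contradicts sections 7.1 and 10.3 on the trigger for the same intervention, in both percentage and reference baseline. That follows from the text alone and needs no assumption.

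The size of the discrepancy does depend on assumptions: relative falls, room-air baselines of 60 to 70, and an oxygen rise of 0 to 20%. Across that range, 7.2.3 treats up to 7.0 points earlier or 10.3 up to 4.2 points earlier. The documents cannot show on which side of the 12.5% crossover patients would fall, so the direction of any effect on treatment frequency is unknown.

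This does not invalidate the randomized comparison. It should still be corrected before the trial relies on it, because it is an instruction to start treatment and the protocol states it in two incompatible ways.

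**What to change.** Amend section 7.2.3 to the dominant rule: a fall of more than 20% below the oxygen-supplemented baseline on either hemisphere, citing Appendix C. Name that baseline in section 10.1, and confirm that the appendix carries the same trigger and letter. If the sponsor actually intends the 10% room-air rule, change 7.1, 10.1 and 10.3 to match it instead. Then use the single trigger to define the events that qualify for treatment under secondary objectives 3 and 4.

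The cost is a wording amendment, an appendix check and a short notice to study staff. The planned AUC categories, the sample size and the analysis methods need no change on this account.

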### 7.2.4 Postoperative Follow Up Period

The postoperative follow up period will continue from PACU or ICU discharge until the patient telephone interview 4 weeks after the surgical procedure. The active elements of the study protocol which involve direct subject interaction during this period include a postoperative day 1 and 3 MMSE and CAM delirium assessments as well as the 4 week post-procedure follow up telephone interview to assess the patient's general state of health following surgery including a query of any need for hospital readmission.

## **Schematic Diagram of Trial Design**

## 7.4 Study Variables

### 7.4.1 Primary Endpoints

The relationship between the observed cerebral oximetry data and a number of predefined intraoperative and postoperative clinical variables will serve as the primary endpoints of this trial. The clinical variables will include the following intraoperative and postoperative (PACU or initial 12 hours of the ICU stay) parameters:

#### 7.4.1.1 Intraoperative:

- Area under the curve of cumulative rSO2 desaturations (AUCrSO2) of progressive categorical degrees that will include the following:
  - < 5% of established room air baseline and oxygen supplemented baseline ○ < 10% of established room air baseline and oxygen supplemented baseline ○ < 15% of established room air baseline and oxygen supplemented baseline ○ < 20% of established room air baseline and oxygen supplemented baseline ○ < 25% of established room air baseline and oxygen supplemented baseline ○ < 30% of established room air baseline and oxygen supplemented baseline ○ < 35% of established room air baseline and oxygen supplemented baseline ○ < 40% of established room air baseline and oxygen supplemented baseline ○ < 60% of absolute measured value (if baseline > 60%) ○ < 55% of absolute measured value (if baseline > 55%) ○ < 50% of absolute measured value (if baseline > 50%) ○ < 45% of absolute measured value (if baseline > 45%) ○ < 40% of absolute measured value ○ < 35% of absolute measured value

○ < 30% of absolute measured value ○ < 25% of absolute

measured value ○ < 20% of absolute measured value

- Area under the curve for cumulative, high and low intraoperative values outside of preestablished, individualized patient blood pressure goals based upon preoperatively observed blood pressure values as well as values clinically accepted to provide adequate organ perfusion. This analysis will be performed for systolic, diastolic and mean arterial pressures (AUCSBP-hi, AUCSBP-low, AUCSBP-cum, AUCDBP-hi, AUCDBP-low, AUCDBP-cum, AUCMAP-hi, AUCMAP-low, AUCMAP-cum). All intraoperative pressure data will be collected with either invasive arterial catheterization [Q30 secs] or non-invasive blood pressure monitoring [Q3 min] as determined by the attending anesthesiologist caring for the subject.
- Area under the curve of intraoperative progressive categorical pulse oximetry (SpO2) desaturations (AUCSpO2) including the following:
  - AUCSpO2 < 95% regardless of intraoperative FiO2 values ○
  - AUCSpO2 < 90% regardless of intraoperative FiO2 values ○
  - AUCSpO2 < 85% regardless of intraoperative FiO2 values ○
  - AUCSpO2 < 80% regardless of intraoperative FiO2 values ○
  - AUCSpO2 < 75% regardless of intraoperative FiO2 values ○
  - AUCSpO2 < 70% regardless of intraoperative FiO2 values ○
- Use of any intraoperative, intravenous vasopressor and/or inotropic agent (as assessed by amount of time in minutes on any IV drug support regardless of dose and assessed by total dose of drug delivered to patient)
- Intraoperative urine output in any patient with an indwelling foley catheter as assessed by mLs urine/kg/hr for total time in operating room
- Need for intraoperative red blood cell transfusion (as assessed by number of RBC units transfused)
- Observed desaturation prompted change in surgical procedure (e.g., the surgery was paused to inflate the collapsed lung to improve systemic tissue oxygenation) ●  
● Occurrence of any intraoperative stroke or transient ischemic attack (as assessed by documented clinical neurological assessment or cerebral imaging study) ● Any

observed intraoperative myocardial ischemia or infarction (as assessed by intraoperative ECG changes and/or myocardial biomarkers (i.e. troponin increase)

- ❶ Area under the curve of any observed intraoperative hyperglycemia ( $AUC_{Glu} > 110 \text{ mg/dL}$ ) in patients with a documented history of either type I or II diabetes mellitus ❶ Any occurrence of intraoperative atrial fibrillation (capturing duration of atrial fibrillation and whether treatment was required)
- ❶ Total time spent in operating room
- ❶ Total amount of narcotic administered in the operating room
- ❶ Total volume of crystalloid administered in the operating room
- ❶ Total volume of colloid administered in the operating room
- ❶ Anti-emetic medications administered in the operating room
- ❶ Surgical procedure performed
- ❶ Time on single lung ventilation ❶

Intraoperative Use of epidural catheter

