- 4) Assess the interventional cohort's preoperative demographics and collected covariates for association with the ease or difficulty of mitigating observed cerebral desaturation events.

Exploratory analyses will include performing all possible comparisons of the two groups based upon all collected perioperative variables to examine the potentially significant relationships between the collected clinical variables representing surrogates of organ perfusion/function and cerebral oximetry desaturations (AUCrSO2). The following exploratory endpoints will be assessed:

- Logistic regression analysis to determine the most relevant AUCrSO2 desaturation value(s) associated with any detrimental clinical outcome(s) monitored in this study
- Logistic regression analysis to determine the most relevant AUC blood pressure values associated with any detrimental clinical outcome(s) monitored in this study
- Comparison of baseline rSO2 values (room air and oxygen supplemented) to all collected clinical variables to assess for possibly significant associations
- Explore the potential impact of rSO2 monitoring on changing the surgical conduct of the procedure

**Methodology:** Single center, prospective, randomized, controlled clinical pilot study

**Number of Subjects:** 100 subjects with balanced randomization (1:1) to control (blinded NIRS data) or intervention (open NIRS data) cohorts

**Main Criteria for Inclusion:** Elderly patients (> 65 years of age) scheduled for a thoracic surgical procedure at UHCMC that will involve SLV.

**Duration of Treatment:** Cerebral oximetry monitoring will begin with an assessment of both room air and oxygen supplemented bi-frontal baseline NIRS values and continue through the surgery to either PACU discharge or the initial 12 hours of post surgical ICU treatment. Mini Mental Status exam testing and Delirium testing with the Confusion Assessment Method will occur preoperatively and postoperatively through post-operative day (POD) #3 (or discharge if that occurs sooner than POD #3).

Enrolled subjects will be followed during the index hospitalization and will undergo a 30 day follow up telephone interview to assess their progress following hospital discharge.

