#### **6.4 Exploratory Objectives**

Exploratory objectives will include performing all possible comparisons of the two groups based upon all collected perioperative variables to examine the potentially significant relationships between the collected clinical variables representing surrogates of organ perfusion/function and cerebral oximetry desaturations (AUCrSO2). The following exploratory endpoints will be assessed:

- Logistic regression analysis to determine the most relevant AUCrSO2 desaturation value(s) associated with any detrimental clinical outcome(s) monitored in this study
- Logistic regression analysis to determine the most relevant AUC blood pressure values associated with any detrimental clinical outcome(s) monitored in this study
- Comparison of baseline rSO2 values (room air and oxygen supplemented) to all collected clinical variables to assess for possibly significant associations

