## 8.5 Device Image

## 8.6 Device Modification

The subjects randomized to the control group will be monitored with a modified device following the acquisition of the baseline NIRS data. The modification involves electronic blinding of the data via an adjustment made to the device by the manufacturer that prevents the active display of the current data and graphic trends on the display console. However, the modified device will still electronically store the acquired NIRS data for later analysis. The use of this modified version of the device will help to reduce investigator bias that might be introduced if a blinder were affixed to the display console.

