### **10.2 Control Group**

The control group will have both room air and oxygen supplemented baselines obtained in an antecedent fashion to establish that they can produce reliable bilateral cerebral oximetry readings. Because it is known that the device may not be able to produce a valid reading in some individuals with pigmented skin or aberrantly located frontal sinuses this step is necessary to insure that all subjects in the control group will produce useful NIRS data. Once the baseline values have been recorded the cerebral oximetry will be monitored in an electronically blinded manner. Specifically, the device will capture data but neither the current values nor the trend will be displayed on the device's display console. The use of this modified version of the device will help to reduce investigator bias that might be introduced if a blinder were affixed to the display console. The baseline values will be obtained prior to the induction of general anesthesia.

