#### 11.3.3 Intraoperative and Immediate Postoperative Clinical Variable Data Collection

##### 11.3.3.1 Intraoperative Clinical Variables Collected

Vasopressor use  
Inotrope use

Amount of narcotic administered  
Time on single lung ventilation

Urine output	Anti-emetic medication administered
Myocardial ischemia	Total crystalloid administered
Stroke or TIA	Total colloid administered
Hyperglycemia $AUC_{Glu} > 110$	Total transfused allogeneic RBCs
Atrial fibrillation	Atrial fibrillation
Use of epidural catheter	
Surgical procedure	$rSO_2$ prompted change in surgery
Time spent in operating room	

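### As listed for collection, an rSO2-prompted change in surgery cannot occur in the blinded control arm, so comparing the arms on it cannot show whether monitoring changes surgical conduct

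*Combined protocol and SAP*

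**What the plan says.** The protocol names this item twice, in different words. Section 7.4.1.1, under the primary endpoints, has "Observed desaturation prompted change in surgical procedure (e.g., the surgery was paused to inflate the collapsed lung to improve systemic tissue oxygenation". It does not say whether the desaturation is cerebral (rSO2) or arterial (SpO2). Section 11.3.3.1, the list of intraoperative variables to be collected, has rSO2 "prompted change in surgery". That list has no other heading for a pause, a lung re-inflation or an altered procedure.

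The arms differ in who can see rSO2. For controls, section 10.2 says "Once the baseline values have been recorded the cerebral oximetry will be monitored in an electronically blinded manner", and that "neither the current values nor the trend will be displayed on the device's display console". Section 8.6 describes a device modification that "prevents the active display of the current data and graphic trends on the display console", and section 11.2.4.3 confirms that it is activated after the two baseline readings. In the intervention arm (section 10.3), the clinicians and a research assistant "will be able to openly monitor the NIRS data", and the assistant alerts the anesthesia clinician to a significant desaturation.

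On analysis, section 6.4 plans "performing all possible comparisons of the two groups based upon all collected perioperative variables". Section 15 assigns the Wilcoxon rank-sum test to the observed clinical data and makes no exception for this item. Section 6.2 sets the pilot's purpose: to find the variables on which the arms differ significantly, so that the multicenter trial can be designed around them. The synopsis adds an exploratory question on the impact of rSO2 "monitoring on changing the surgical conduct of the procedure". Section 6.4 does not repeat that question.

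**The concern.** A variable defined by what prompted an action can be compared between arms only if the prompt is available in both. Here the prompt named in section 11.3.3.1 is available in one arm. A control subject whose lung is re-inflated because SpO2 fell has had the same surgical interruption as an intervention subject whose lung is re-inflated because rSO2 fell. Only the second fits the listed item.

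Two things are at stake. First, the pilot screens variables by between-arm significance, and this one can move in a single direction for reasons unrelated to benefit or harm. Second, whether monitoring alters surgical conduct is a question about the total rate of interruptions with and without the monitor. No listed item gives that rate for controls, and it may be hard to reconstruct afterwards.

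**Working it through.** **Step 1: the two wordings side by side.**

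| Reading | Control events possible? | Listed item that captures them? |
|---|---|---|
| rSO2-prompted only (11.3.3.1) | No: rSO2 is hidden after the pre-induction baselines | Not applicable |
| Any observed desaturation (7.4.1.1), including SpO2 | Yes: nothing in the documents blinds SpO2 in either arm | None in 11.3.3.1 |

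On the first reading the control count is a structural zero. On the second it is not, but the sections disagree. The definition also still rests on the prompt, so clinicians in the open arm have one more trigger to act on and to record.

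**Step 2: what a control count of zero does to the test.** The protocol gives no event rate, effect size or power figure for this item, so there is no stated result to reproduce. Inputs: 100 subjects randomized 1:1 (section 7.1), so n = 50 per arm; the rank-sum test and the 0.05 level (section 15). Two-sided testing is assumed, since sidedness is not stated, and section 15 attaches the 0.05 level to its regression sentence.

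For a yes/no variable with k/50 against 0/50, let p̄ = k/100. The tie-corrected rank-sum statistic is

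z = (k/50) / √[ p̄(1 − p̄) × (2/50) × (100/99) ].

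For k = 4: z = 0.08 / √(0.04 × 0.96 × 0.04 × 1.0101) = 0.08 / 0.0394 = 2.03, so p = 0.042.

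The exact rank-sum distribution for a yes/no variable is hypergeometric, which is Fisher's test. With a zero in one of two equal arms, the two-sided p is 2 × C(50,k) / C(100,k). For k = 4: 2 × 230,300 / 3,921,225 = 0.117.

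| Intervention events (control 0/50) | Rank-sum, normal approximation | Exact (Fisher) |
|---|---|---|
| 3/50 | 0.080 | 0.242 |
| 4/50 | 0.042 | 0.117 |
| 5/50 | 0.022 | 0.056 |
| 6/50 | 0.012 | 0.027 |

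A continuity correction moves the approximate value at 4/50 only to 0.043. The threshold is therefore four events with the approximation and six with the exact version. Section 15 does not say which version is meant.

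**Step 3: how often that would happen.** This needs the rate of rSO2-prompted changes in the intervention arm, which is an assumption. The chance of significance is the binomial probability of at least 4 (approximate) or at least 6 (exact) events in 50.

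| Assumed intervention rate | Approximate | Exact |
|---|---|---|
| 5% | 24% | 4% |
| 10% | 75% | 38% |
| 15% | 95% | 78% |
| 20% | 99% | 95% |

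These chances do not depend on the true rate of interruptions in controls. For illustration, suppose 10% of subjects in each arm (0.10 × 50 = 5) have the lung re-inflated, and all five in the open arm are attributed to rSO2. The item then reads 5/50 against 0/50 although the arms do not differ.

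**Step 4: the same test on an all-trigger count.** If interruptions were counted in both arms whatever the trigger, equal true rates of 5% to 30% (assumed) would give a false-positive rate of 4.3% to 5.0% with the approximate rank-sum test and 0.7% to 3.1% with Fisher, by exact enumeration. Power would be modest. The pooled two-proportion formula is Φ{[d√50 − 1.96√(2p̄(1 − p̄))] / √[p₁(1 − p₁) + p₂(1 − p₂)]}, with d = p₂ − p₁ and p̄ the mean of p₁ and p₂. For 10% against 20% it gives Φ[(0.707 − 0.990)/0.500] = 29%. For 10% against 30% it gives Φ[(1.414 − 1.109)/0.548] = 71%.

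**The case against.** The strongest reply is that the endpoint definition is in section 7.4.1.1, which does not mention rSO2. The same section uses the word desaturation for SpO2, and its example aims at systemic oxygenation. On that reading a pause prompted by falling SpO2 counts in either arm. This stands, and a reader who infers that the endpoint is zero in controls on any reading goes beyond the documents. The structural zero belongs to the wording in section 11.3.3.1.

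Section 11.3.3.1 is also only a list of short headings, one of which (atrial fibrillation) is printed twice, and the case report form is not among the documents. The list shows that no such item is named. It does not prove that a control-arm pause would go unrecorded. This stands too, and is a reason to reconcile the sections explicitly.

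Third, the intervention-arm count has a proper descriptive use: how often open monitoring led to a change. It fits secondary objective 3, on the frequency and efficacy of mitigating interventions. That is right, and the fix keeps it. But sections 6.4 and 15 do not exempt the item from between-arm comparison, and nothing marks it as descriptive only.

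Fourth, time on single lung ventilation, operating-room time and the SpO2 areas under the curve are collected in both arms. They bear on surgical conduct indirectly, but none counts pauses or re-inflations.

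Finally, a reader might infer that the item is bound to be flagged as significant. It is not: blinding fixes the direction of the difference, and the intervention count decides the p-value. The interventions described in section 10.3 include no surgical pause or re-inflation, so the count could be small.

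**Conclusion.** The point holds for the item as section 11.3.3.1 lists it. Control events are then impossible, the planned comparison can go one way only, and it cannot answer the synopsis question about surgical conduct. If section 7.4.1.1 was meant more broadly, what remains is a conflict between the two sections, no listed item for control events, and a prompt-based definition that still favors recording in the open arm.

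The size depends on an event rate that the documents do not give. Between four and six intervention-arm events would produce a significant difference, according to the version of the test. The figures assume 50 analyzed subjects per arm, one yes/no outcome per subject and a two-sided 0.05 level. The documents do not support saying that significance is automatic, or that four events suffice whichever version is used.

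Severity is low to moderate: one item among many in a pilot, serving an exploratory aim that appears only in the synopsis.

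**What to change.** Reconcile sections 7.4.1.1 and 11.3.3.1 with a single definition that does not depend on the prompt: any interruption or change of the planned procedure made to improve oxygenation, recorded in the same way in both arms. For each event, record the time and the trigger (SpO2, rSO2, hemodynamic or surgical). In section 15, state that the all-trigger count is compared between arms and whether the rank-sum test is exact or approximate. State also that the rSO2-triggered count is reported descriptively for the intervention arm only.

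This changes recording and analysis, not patient care. It costs one reworded endpoint, one field with a trigger code and a few more entries per case. It makes the contrast interpretable, but at 50 per arm only a large difference would be detected reliably, so the result should be presented as an estimate with its confidence interval.
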